Using Financial Incentives and Screening to Increase Engagement with
Mental Health Services among College Students in Chennai, India
Pre-analysis plan

12 February 2025

1 Introduction

This study will evaluate the effectiveness of interventions to increase engagement with mental health services among a sample of college students in Chennai, India. We have partnered with an arts and science college for women in Chennai, where the study will be conducted. The sample will be recruited in person during college hours.

We will introduce the study to all students present in the classrooms at the time allotted by the college administration and obtain consent from those interested after screening them for age eligibility (between the ages of 18 and 30). Study participants will then complete a survey via a Qualtrics link using their cell phones. The survey will include questions about demographics, perceptions of their own mental health, mental health treatment history, and the PHQ-ADS, a standardized composite screening tool for depression and anxiety.

The experimental design is an RCT with 4 groups, randomized at the individual level. The investigators will measure interest in, and take-up of, psycho-therapy at the individual level. We will also collect data on other activities that capture engagement with mental health care, such as take-up of a cellphone app that provides tools to improve mental health, and seeking information about mental health.

2 Sample and Treatment

2.1 Sample Population

The experimental sample consists of college students at a college in Chennai who (i) are at least 18 years old, (ii) are present in the classrooms when we visit, and (iii) consent to participate in the study. We will attempt to visit all classrooms (i.e., all majors and years) over the course of the study. However, we rely on the college administration to make students available and scheduling constraints on the part of the college may keep us from visiting all classrooms. In addition, attendance rates on a given day are well below 100% (and as low as 50% during our scoping visits). Thus, the final experimental sample will be substantially smaller than the full college student population of approximately 3000.

2.2 Treatments

Treatments are randomized at the individual level, stratified by categories of PHQ-ADS scores. Treatment status will be revealed via the survey administered through students' mobile phones. Participants will be randomized to four conditions:

1. **Control:** The control group will (a) watch a video introducing them to the mental health services available in the college, including introductory videos of the counselors, (b) have access to therapy at no cost for the duration of the study via their college counselors and additionally at SCARF, a mental health center in Chennai, and (c) be given links to book a therapy session or download a mental health app.
2. **Screening:** In addition to the interventions in the control group, students in the screening group will receive feedback on their PHQ-ADS score and recommendations based on that. In particular, they will be informed whether their responses to the PHQ-ADS questions fit in the standard risk categories of no, mild, moderate, or severe distress and corresponding recommendations for whether to make an appointment with a counselor/therapist.
3. **Rewards:** In addition to the interventions in the control group, students in the rewards group will be provided with a cash payment of Rs. 500 (USD 5.70 at market exchange rates) for attending a (first) therapy session.
4. **Screening and rewards:** Students in this group will receive both interventions, i.e., both the screening information and the reward described above.

For ethical reasons, participants with PHQ-ADS scores of 30 or above (indicating severe risk of depression and anxiety) in the non-screening treatment arms will also be informed of their scores at the end of the survey. For outcome variables measured within the survey, we will treat these participants as though they are part of the group to which they are randomly assigned. One outcome variable (completing the process to make an appointment for therapy) is measured after the conclusion of the participant survey. For this outcome variable, we will separately run regressions both including and excluding these individuals.

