3.1 Primary Outcomes

We have two primary outcomes:

1. **Expressing interest in therapy.** This consists of students answering “yes” when asked in the survey if they would like to book an appointment with a counselor, or if students answer “yes” when asked in the survey if they would like to be contacted by a study counselor to discuss mental health and therapy.
2. **Making an appointment.** If a student actually makes an appointment with a counselor (measured using the administrative records from the counseling offices)

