3.2 Secondary Outcomes

The secondary outcomes of the study include the following:

1. **Take-up of mental health app.** This is measured in two ways: participants expressing interest in accessing a mental-healthcare app in the survey, and participants actually clicking a link to download the app.
2. **Demand for information about mental health.** This is measured in two ways: participants expressing interest in receiving more information about mental health, and participants actually clicking a link to access the information.
3. **Attendance of therapy sessions.** We will collect data from the administrative records of the counselling office on whether participants actually attended a therapy session, as well as the number of sessions attended.
4. **Other variables.** We will also report exploratory analyses and mechanism tests including: (i) whether participants report in the survey if they would consider seeking therapy in future; (ii) what steps they report they would take to take care of their mental health in future; (iii) reported motivating/inhibiting factors for taking up therapy and perceptions of therapy.

4 Empirical analysis

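### Section 2.2 counts only one post-survey outcome, but therapy attendance and number of sessions also follow the severe-score disclosure and have no matching analysis

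*Combined protocol and SAP*

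**What the plan says.** Section 2.2 provides, for ethical reasons, that severe scorers (PHQ-ADS of 30 or above) "in the non-screening treatment arms will also be informed of their scores at the end of the survey". It then sets two rules.

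- In-survey outcomes: severe scorers are analysed in the arm they were randomised to.
- One exception: "One outcome variable (completing the process to make an appointment for therapy) is measured after the conclusion of the participant survey". The handling is: "For this outcome variable, we will separately run regressions both including and excluding these individuals".

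Section 3.1 defines the appointment outcome as "measured using the administrative records from the counseling offices". Section 3.2 lists attendance of therapy sessions as a secondary outcome, also from the counselling office's records. It covers "whether participants actually attended a therapy session, as well as the number of sessions attended".

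Section 4.1 runs the pooled-screening regression and the saturated regression for every outcome. Neither section 4.1 nor section 4.2 gives a rule for disclosed severe scorers.

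**The concern.** The sponsor already accepts that the safety disclosure can blur the screening contrast for outcomes that follow it; that is why bookings get a second regression. The same reasoning covers attendance and number of sessions, but the text leaves them out. They fit neither rule in section 2.2, being neither measured within the survey nor the single named exception.

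Attendance is the outcome closest to receiving care, and a first attended session is what the Rs. 500 reward pays for. As the plan stands, its screening estimate would be reported without saying that some of the comparison group had also received score information. A handling rule chosen after the data are seen would not be pre-specified.

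**Working it through.** **Step 1: timing of each outcome against the disclosure.**

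| Outcome | Source | After the disclosure? | Handling in section 2.2 |
|---|---|---|---|
| Interest in therapy (3.1) | Survey answers | No, treated as in-survey | As assigned |
| Making an appointment (3.1) | Counselling-office records | Yes, stated | With and without severe scorers |
| Any attendance (3.2) | Counselling-office records | Yes | None stated |
| Number of sessions (3.2) | Counselling-office records | Yes | None stated |

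The offer of a booking is made in the survey, and the plan itself places the completed booking after it. Attending a session that results from the offer comes later still. The count of one is therefore too low by two measures.

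**Step 2: which contrast is affected.** The disclosure goes to Control and Rewards, the two arms that form the comparison side of the pooled-screening indicator in section 4.1. In the saturated model it reaches the Control reference group. The Rewards-versus-Control comparison has the disclosure on both sides, so the issue belongs to the screening contrasts.

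**Step 3: possible size.** The plan states no figure to reproduce. Three inputs are needed, and all are assumptions:

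- s, the share scoring 30 or above. Section 4.2 says only that it is expected to be small; 2% and 5% are used.
- k, the screening effect in severe students divided by the effect in the others; 1, 2 and 4 are used.
- d, the fraction of the severe students' screening effect that the late disclosure reproduces; 0, 0.5 and 1 are used.

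Set the effect in non-severe students to 1.

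- Effect against an undisclosed control: (1 − s) + s·k
- Effect with the disclosure: (1 − s) + s·k·(1 − d)
- Proportion lost: s·k·d / [(1 − s) + s·k]

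Lowest non-zero case: s = 0.02, k = 1, d = 0.5 gives 0.01 / 1.00 = 1.0%. Highest case: s = 0.05, k = 4, d = 1 gives 0.20 / (0.95 + 0.20) = 0.20 / 1.15 = 17.4%.

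| s | k | d = 0 | d = 0.5 | d = 1 |
|---|---|---|---|---|
| 2% | 1 | 0 | 1.0% | 2.0% |
| 2% | 2 | 0 | 2.0% | 3.9% |
| 2% | 4 | 0 | 3.8% | 7.5% |
| 5% | 1 | 0 | 2.5% | 5.0% |
| 5% | 2 | 0 | 4.8% | 9.5% |
| 5% | 4 | 0 | 8.7% | 17.4% |

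**Step 4: what a restricted regression estimates.** In this model, limiting the sample to PHQ-ADS below 30 always returns 1.00, the effect in non-severe students. With s = 5% and k = 4:

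- Undisclosed effect: 0.95 + 0.20 = 1.15
- All-participants estimate at d = 1: 0.95
- All-participants estimate at d = 0.5: 0.95 + 0.10 = 1.05

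The restricted value lies above the all-participants estimate in one case and below it in the other, and equals 1.15 in neither. It is free of the disclosure, but it does not measure the loss.

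**The case against.** The strongest reply is that nothing is invalid. Where section 2.2 is silent, section 4.1's regression by assigned arm applies, and it estimates a genuine effect of assignment. Attendance is secondary, the affected primary outcome already has its with-and-without regressions, and bookings give indirect evidence on attendance. All of this stands, and it limits the point to a wrong list and a missing companion analysis.

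It can also be said that the single outcome was meant to refer to primary outcomes only. Section 2.2 does not say so, and on that reading attendance still has no stated handling.

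Three stronger readings are tempting, but the documents do not support them:

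- **Link clicks.** A reader might infer that outcomes such as "participants actually clicking a link to download the app" also follow the disclosure. The plan does not say when clicks occur or are recorded, so they cannot be counted as affected.
- **A false gap between bookings and attendance.** A reader might infer that the safety rule could make screening appear to raise bookings but not attendance. The same disclosure precedes both, so the two all-participants regressions are both exposed. A misleading comparison would arise only if a booking result excluding severe scorers were set beside an attendance result including them.
- **Dilution as a fact.** It requires the late disclosure to change behaviour. Screening arms receive a risk category and a recommendation, whereas section 2.2 says only that the other arms' severe scorers are told their scores. Full equivalence (d = 1) is therefore best read as an upper limit.

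**Conclusion.** The point holds in a limited form. Section 2.2 miscounts the post-survey outcomes, so any attendance and number of sessions lack the handling that the plan itself considers necessary for bookings. Their screening coefficients compare against a partly screened group. They may be pulled towards zero relative to an undisclosed control, provided that late disclosure acts in the same direction as screening.

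The size cannot be computed from the documents. It is nil if the disclosure has no effect. It is roughly 1-17% of the pooled effect for a 2-5% severe share, k between 1 and 4, and half or full reproduction of the screening effect. A reader might infer a much larger loss by assuming a high severe share and a far stronger effect in severe students, but section 4.2 expects few severe scorers. The correction should be made; the primary analysis is not undermined.

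**What to change.** In section 2.2, replace the reference to one outcome variable with a list: making an appointment, any attendance, and number of sessions. For each, pre-specify:

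1. the all-participants regression by assigned arm, stating that severe scorers in Control and Rewards had been told their scores; and
2. a companion regression restricted to PHQ-ADS below 30 in all four arms.

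The restriction should apply to every arm because section 2.2's exclusion, read literally, removes severe scorers only from the non-screening arms and would unbalance the comparison. The score is collected before treatment (section 4.1) and its categories are used for stratification (section 2.2), so restricting on it in all arms keeps the randomised comparison.

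Describe the companion as the effect in students unaffected by the disclosure, not as a measure of the dilution.

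The cost is a wording change, a few extra regressions on data already planned for collection, and slightly wider intervals in the restricted version.

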4.1 Main regression specification

Pooled treatment effects. Our main specification will be a linear regression of outcomes on the ‘pooled’ treatment assignment, separately for the screening treatment and rewards treatment. That is, define

$$\begin{aligned} \text{Pooled screen}_i &= \text{Screen}_i + \text{Screen and rewards}_i \\ \text{Pooled rewards}_i &= \text{Rewards}_i + \text{Screen and rewards}_i, \end{aligned}$$

where Screen_i is an indicator variable for i being assigned to the screening group, Rewards_i is an indicator variable for i being assigned to the rewards group, and $\text{Screen and rewards}_i$ is an indicator variable for i being assigned to the combined screening and rewards group.

To identify the effect of the pooled treatments on the outcome variables, we will run the following regression specification, separately for each pooled treatment and outcome variable:

$$Y_i = \alpha + \beta T_i + X_i' \lambda + \epsilon_i$$

where Y_i represents the outcomes for individual i described above, $T_i \in \{\text{Pooled screen}_i, \text{Pooled rewards}_i\}$ represents the pooled treatment indicators described above. X_i is a vector of controls consisting of the limited set of variables collected in the survey prior to treatment. This includes categories of PHQ-ADS scores (no risk, mild risk, or moderate-to-severe risk), whether participants report that their family would be supportive of seeking therapy, their current mood, their perception of their current and previous mental health and well-being, whether they have received mental health care in the past, interest in therapy at baseline, and a measure of their financial status.

Fully saturated model. For each outcome, we will also report a “saturated” regression which breaks up the effects by each of the treatment cells:

$$Y_i = \alpha + \beta_1 \text{Screen}_i + \beta_2 \text{Reward}_i + \beta_3 \text{Screen and Reward}_i + X_i' \lambda + \epsilon_i$$

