4.2 Heterogeneity analysis

Heterogeneity by baseline mental health status. For our primary outcome and for selected secondary outcomes such as take-up of the app, we will analyze heterogeneity by baseline mental health status, as measured by the PHQ-ADS. This heterogeneity is policy-relevant, because policy-makers may especially value students at high risk of anxiety and depression receiving therapy. It also conceptually relates to our treatments, in that screening might be expected to cause more positive selection on symptoms of depression and anxiety while rewards have ambiguous selection effects.

The standard cutoffs in scores in the PHQ-ADS scale in the literature are 10-19 for mild symptoms, 20-29 for moderate symptoms, and 30 or higher for severe symptoms. We will combine the moderate and severe categories in our analysis, as only a small share of students are expected to show severe symptoms.

We will estimate the following regression:

$$Y_i = \alpha + \beta T_i + \gamma T_i \times \text{Mild}_i + \theta T_i \times \text{Moderate or Severe}_i + \lambda X'_i + \epsilon_i$$

for each of the pooled treatment indicators and outcome variables. The vector of controls X_i includes the indicator variables Mild_i and $\text{Moderate or Severe}_i$.

We will also run a model which interacts the treatments with a continuous measure of the PHQ-ADS score:

$$Y_i = \alpha + \beta T_i + \gamma T_i \times \text{PHQ-ADS}_i + \lambda X'_i + \epsilon_i$$

where X_i is the vector of controls now including the continuous measure of PHQ-ADS score.

Heterogeneity by other characteristics. As exploratory analyses, we will examine heterogeneity by other baseline characteristics, such as participants' financial status, their perception of their mental health status, and their major sources of stress.

Heterogeneity by other characteristics.

5 Funding and Human Subjects Review

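### The excluding regression for appointments drops severe-risk students from the non-screening arms only, so it no longer compares randomised groups and favours screening if severe students book more often.

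*Combined protocol and SAP*

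**What the plan says.** Section 2.2 describes the randomisation: "Treatments are randomized at the individual level, stratified by categories of PHQ-ADS scores". It then makes an exception on ethical grounds: "participants with PHQ-ADS scores of 30 or above (indicating severe risk of depression and anxiety) in the non-screening treatment arms will also be informed", with the disclosure coming at the end of the survey. In-survey outcomes are analysed by assigned group. For the one outcome that Section 2.2 counts as measured after the survey, completing a therapy appointment, the rule is: "For this outcome variable, we will separately run regressions both including and excluding these individuals". The group referred to is the one just defined, that is, scorers of 30 or above in Control and Rewards. Nothing in the plan removes scorers of 30 or above from Screening or from Screening and rewards.

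The outcome is one of two primary outcomes (Section 3.1). The control vector in Section 4.1 includes "categories of PHQ-ADS scores (no risk, mild risk, or moderate-to-severe risk", with no separate severe category. Section 4.2 uses the same merged category in its interaction model, because "only a small share of students are expected to show severe symptoms". The plan does not say whether the including or the excluding run is primary.

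**The concern.** Whether a student is dropped depends on the assigned arm as well as on a baseline score. After exclusion, the screening arms contain all levels of symptoms and the non-screening arms stop at 29. If severe students book at a different rate from the rest, the pooled screening coefficient differs from zero even when screening does nothing. The same shift enters the Screen and the Screen-and-rewards coefficients of the saturated model. It enters undiluted in the interaction of screening with the moderate-or-severe category, if the excluding run is extended to that model.

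Readers are likely to lean on this run. The including run preserves randomisation, but severe students in the non-screening arms also learn their scores, which would tend to dilute the screening contrast. A larger estimate in the excluding run would naturally be read as the effect with that contamination removed. As written, it would mix that removal with selection, and the data could not separate the two.

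**Working it through.** **What follows from the text alone.** Within the merged moderate-to-severe category, the excluding run compares moderate plus severe students (screening arms) with moderate students only (non-screening arms). That needs no assumed number.

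**Inputs for the size.** The plan states no booking rates, severe share, sample size or allocation ratio, so there is no figure of its own to reproduce. Assumed: equal allocation; no true screening effect; 45% no risk, 30% mild, 25% moderate plus severe; booking 3%, 5% and 8% in no-risk, mild and moderate students. The severe share and severe booking rate are varied.

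**Formulas.** Let s and m be the severe and moderate shares, M = s + m, and p_s, p_m the booking rates.

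- Unadjusted bias = mean booking over all students − mean booking over non-severe students.
- Gap in the merged category: G = (s/M)(p_s − p_m). This is also the bias in the moderate-or-severe interaction, since the no-risk category has none.
- With the three-category control, least squares weights each category by n1·n0/(n1 + n0). The merged category gets w = A/[A + (1 − M)/2], where A = Mm/(M + m). Adjusted bias = G × w.

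**Worked case: s = 10%, m = 15%, p_s = 20%.**

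- Screening arms: 0.45×3 + 0.30×5 + 0.15×8 + 0.10×20 = 6.05%.
- Non-screening arms: (1.35 + 1.50 + 1.20)/0.90 = 4.50%.
- Unadjusted bias: 6.05 − 4.50 = **+1.55 points**.
- G = (10/25) × 12 = 4.8 points.
- A = 0.25×0.15/0.40 = 0.09375; w = 0.09375/(0.09375 + 0.375) = 0.20.
- Adjusted bias: 4.8 × 0.20 = **+0.96 points**, against a non-screening rate of 4.50%.

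**Range.** False-positive rates come from 1,000 simulated trials per row at N = 1500, with the three-category control, robust standard errors and a two-sided 5% test. Simulation error near 5% is √(0.05×0.95/1000) = 0.7 points.

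| Severe share | Severe booking | Unadjusted bias (points) | Adjusted bias (points) | Interaction bias G (points) | False positives, pooled screening |
|---|---|---|---|---|---|
| 5% | 20% | +0.77 | +0.55 | +2.4 | 8.0% |
| 5% | 30% | +1.27 | +1.01 | +4.4 | 13.1% |
| 10% | 20% | +1.55 | +0.96 | +4.8 | 13.7% |
| 10% | 30% | +2.55 | +1.76 | +8.8 | 35.1% |
| 15% | 30% | +3.86 | +2.11 | +13.2 | not simulated |
| 10% | 8% (as moderate) | +0.35 | 0 | 0 | 4.2% |
| 10% | 4% (below moderate) | −0.05 | −0.32 | −1.6 | 4.9% |

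**Second set of assumptions.** Booking of 5/8/15/30% across the four levels, severe shares of 3%, 7% and 12%, and moderate shares of about 14%, 15% and 17.5%. G is (3/17)×15 = 2.6, (7/22)×15 = 4.8 and (12/29.5)×15 = 6.1 points. The weights w are 0.156, 0.186 and 0.238, so the adjusted bias is +0.4, +0.9 and +1.45 points. Simulated false-positive rates at N = 1500 are about 5–6%, 9.5% and 16–17% for pooled screening, and 8–10%, 17–18% and 26–30% for the interaction.

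**Other coefficients.** In the worked case the Screen and Screen-and-rewards coefficients both shift by +0.96 points. The pooled rewards coefficient does not move, because Control and Rewards lose the same students.

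**Symmetric exclusion.** Dropping scores of 30 or above from all four arms gives a bias of 0 in every scenario. The simulated false-positive rate in the first set is 3.5% to 5.7% across N = 1000 to 2000.

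**The case against.** - **Direction.** The bias is upward only if severe students book more often than moderate ones (or, unadjusted, than the rest). The plan gives no rates. This stands, and the conclusion is worded conditionally. The plan's own reasoning makes upward the likelier direction: "screening might be expected to cause more positive selection on symptoms of depression and anxiety".
- **Other controls.** Section 4.1 also adjusts for baseline interest in therapy, mood, perceived mental health, past care, family support and financial status. Several of these may track severity and booking, so the bias under the full vector could be smaller than shown, by an unknown amount. The continuous-score model in Section 4.2 may also absorb part of it. None of these is a severe indicator, so none can be relied on to remove it.
- **Size.** At a 3% severe share the overall false-positive rate is close to nominal. The large figures need both a sizeable severe share and a wide gap in booking. This stands.
- **Scope.** The interest outcome, the including run and the rewards contrast are untouched. The plan neither calls the excluding run the clean version nor names it primary. This limits the damage to the screening coefficients in one of two paired analyses of a primary outcome.
- **Intent.** The authors may have meant to drop all scores of 30 or above. The text does not say so, and code written from it would make the one-sided exclusion.

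**Conclusion.** The concern holds. The loss of comparability between screened and unscreened students follows from the wording of Section 2.2 and rests on no assumption. Its sign and size rest on the assumed severe share and booking rates. Where severe students book more than moderate ones, the illustrative adjusted bias runs from about +0.4 to +2.1 points, and the pooled-screening false-positive rate at N = 1500 from near nominal to about a third. The moderate-or-severe interaction is affected most. With equal booking rates the adjusted bias is zero; with lower rates it is slightly negative. Because this is a primary outcome and the repair is trivial, the text should be corrected before the regression is run.

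**What to change.** Replace the exclusion sentence in Section 2.2 with wording such as:

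> *For outcomes measured after the survey, the excluding analysis drops every participant with a baseline PHQ-ADS score of 30 or above, in all four arms. The regression on all randomised participants is the intention-to-treat analysis and is primary; the excluding analysis is supportive and applies to students scoring below 30. The pooled rewards contrast needs no exclusion.*

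The score is measured before treatment, so this keeps the randomised comparison. The reference to all post-survey outcomes is deliberate: therapy attendance in Section 3.2 also comes from counselling-office records, yet Section 2.2 counts only one such outcome.

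An alternative is to keep the one-sided exclusion and add a separate severe indicator to the controls. With no severe students left in the non-screening arms, that category then has n0 = 0 and zero weight in the screening coefficient, so the comparison is in effect the same. Symmetric exclusion is easier to explain.

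The cost is one sentence and one line of code. The excluding run loses the severe students in the screening arms, which is half the severe share under equal allocation (5% of the sample if 10% are severe). It then says nothing about screening in severe students. The one-sided version cannot inform that question either, since it keeps no unscreened severe students.
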